- Patients will be asked if they are pregnant by research staff before participation in the study.
- Known contradictions or sensitivities to study medication (oxymetazoline)
- Ocular surgery within the past 3 months or refractive surgery within the past six months
- Grossly abnormal lid margins, anatomical abnormalities, previous eyelid or orbital surgery
- Variable ptosis or eyelid position (e.g., myasthenia gravis, thyroid eye disease, or blepharospasm)
- Significant pre-existing ptosis of any cause (defined as MRD1 < 1mm)
- Any ocular or systemic condition that, in the opinion of the investigator, would confound study data, interfere with the subject's study participation, or affected the subject's safety or trial parameters
- Presence of an active ocular infection
- Prior (within 5 days of beginning study treatment) use of eye whiteners (eg, vasoconstrictors), decongestants, antihistamines (including over the counter and herbal topical ophthalmic medications), phenylephrine dilating drops, any other topical ophthalmic agents
- Inability to sit comfortably for 15 30 minutes

Subject Identification and Recruitment

Potential subjects will be identified during their normal clinic visit at the Bascom Palmer Eye Institute, primarily within the Oculoplastics department. The attending physician will ask eligible patients if they are interested in hearing about the study. No phone calls for recruitment will be made prior to the regular clinic visit. Patients may additionally be referred from other providers within the Bascom Palmer Eye Institute during their regular visits or from the emergency room. Bascom Palmer employees and University of Miami Miller School of Medicine students would also be invited to participate if interested.

Participants who qualify for the study and express an interest in participating will have the study explained to them by a research study member and can ask questions. They will receive information on risks and benefits to research participation. They will receive a copy of the consent form and if desired may be able to take the consent form home prior to signing for

further consultation. Those who are interested in participation will be given a scheduled appointment to meet with research staff.

Upneeq[™] Drug Product

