Upneeq[™] is an FDA approved drug for the treatment of ptosis. It is available in a drop formulation. This agent should be considered exempt from IND requirements as the study is using the drug in realm of FDA indications and meets the below IND criteria.

• The research is not intended to be reported to the FDA as a well-controlled study in support of a new indication for use nor intended to be used to support any other significant change in the labeling for the drug.

• The research is not intended to support a significant change in the advertising for the product.

• The research does not involve a route of administration or dosage level or use in a patient population or other factor that significantly increases the risks (or decreases the acceptability of the risks) associated with the use of the drug product.

• The research is conducted in compliance with the marketing limitations described in 21 CFR §312.7.

Drug insert is available and attached to the IRB protocol.

Procedures Involved

We anticipate that procedures listed below will take about 30 to 40 minutes per patient. Except as noted, the procedures below are not considered standard of care and are being conducted for the study alone.

Part 1: Pre-treatment data collection

- Patients will complete a pre-treatment survey to evaluate the perceived baseline eye appearance.
- Patients will undergo pre-treatment baseline photography. Images will be taken in a room with the same conditions.
- An Ipad (Apple Inc, Cupertino, California, U.S.A.) with the Upneeq software app will be used. This app directs subjects to a standardized position and distance from the Ipad to measure the MRD1 and MRD2 in each eye. The subjects will focus on the Ipad with their eyes in primary gaze.
- All photographs will be taken with the dedicated Ipad camera, which will use standardized aperture, shutter speed, and exposure time.
- Photographs will be recorded and saved as JPG files (1200 9 797 pixels, 24-bit, RGB) in a locked folder. When not in use, the Ipad and accompanying software will be secured in a locked drawer.

Part 2: Upneeq[™] application

- Subjects will be randomized to receive either Upneeq[™] or balanced saline placebo in both eyes.
- Based on the randomization results, the examiner will apply Upneeq[™] eye drops or saline to the subject's eyes.

Part 3: Post-treatment data collection

- Subjects will wait 2 hours after they receive eye drops.

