- Subjects will be photographed at 2 hours after drop instillation according to the procedure described above. This will allow Upneeq to reach its average time for maximum effect.
- Patients will complete a post-treatment survey to evaluate the perceived change in eye appearance following Upneeq[™] administration.

Part 4: Data analysis

- Data will be recorded and stored in a secure Microsoft Office Excel (Microsoft Corporation, Redmond, WA, U.S.A.) spreadsheet. Data will be graphically analyzed and represented with Adobe Photoshop (Adobe, Inc., San Jose, CA, U.S.A).
- Data assessed will involve assessing pre and post-treatment MRD1 and MRD2, investigator-assessed measurements of conjunctival color including the Validated Bulbar Redness Scale and patient-reported outcome measures such as those measured through the FACE-Q survey or other patient perceptions of the drop and changes in appearance before and after drop instillation.
- User performing analysis will be blinded to which patients received study drug or control.

No additional follow-up outside of the patient's next routine clinic visit will be needed. Patients who do have symptoms concerning any post-procedural complications will be instructed to notify study staff immediately. A phone number will be provided. Clinical examination post-procedure will be at Bascom Palmer Eye Institute.

Outcomes Measured

Primary outcome:

Outcome Measure Title: Change in palpebral fissure height

Outcome Measure Description: Palpebral fissure height will be calculated from the sum of marginal reflex distance 1 and 2 measured from the photograph by Ipad software and recorded by investigators.

Outcome Measure Timeframe: Baseline prior to drop administration, Day 1

Secondary outcomes:

Outcome Measure Title: Change in eye redness

Outcome Measure Description: Scoring of ocular redness from clinical photographs will be performed by investigators on a 0 - 100 unit scale as compared to standardized reference photographs (0 = no redness, 100 = very red). Images may also be analyzed quantitatively using software to calculate changes in redness between photographs.

Outcome Measure Timeframe: Baseline prior to drop administration, Day 1

Outcome Measure Title: Change in Patient-reported eye appearance

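### The primary outcome has no replicate frames, averaging or frame-selection rule, so residual momentary lid variation costs precision that three photographs per time point would partly recover

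*Combined protocol and SAP*

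**What the plan says.** Under Outcomes Measured, the primary outcome is the change in palpebral fissure height, described as follows: "Palpebral fissure height will be calculated from the sum of marginal reflex distance 1 and 2 measured from the photograph by Ipad software".

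The two photographic sessions are set out under Procedures Involved. Part 1 says: "Patients will undergo pre-treatment baseline photography. Images will be taken in a room with the same conditions". Part 3 says: "Subjects will be photographed at 2 hours after drop instillation according to the procedure described above". Neither part states how many frames are taken, whether readings are averaged, when a frame is retaken, or which frame supplies the value.

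Part 1 does standardise the capture. On geometry: "This app directs subjects to a standardized position and distance from the Ipad to measure the MRD1 and MRD2 in each eye". On gaze: "The subjects will focus on the Ipad with their eyes in primary gaze". On the camera: "All photographs will be taken with the dedicated Ipad camera, which will use standardized aperture, shutter speed, and exposure time". The exclusion criteria also remove people whose lid position varies because of disease, such as myasthenia gravis or blepharospasm. Partial blinks and brow lift in otherwise eligible subjects are not mentioned.

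**The concern.** Lid height can shift from one moment to the next with a partial blink or a raised brow. A value read from one frame carries that moment's deviation, and a change score carries the deviations of two frames. Fixation, positioning and camera settings remove other sources of variation but not these.

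The stake is precision on the primary outcome. The Local Number of Subjects section caps enrolment at about 114 because of limits on time and resources, so precision cannot easily be bought with more subjects. It can be bought by measuring each subject better at visits that already take place. A lesser issue is that, if the operator takes a further shot, nothing says which one is used.

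**Working it through.** **The plan's own figure.** The only figure to check against is the sample size of 114. The Statistical Analysis Plan gives no effect size, SD, power or dropout for it, so it cannot be reproduced, and no measurement SD can be recovered from it.

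**Inputs.** Two sessions per subject (Procedures Involved, Parts 1 and 3). One measured frame per session is the literal reading of the outcome sentence. The frame-to-frame SD *s* and the SD of true change *t* are not in the documents. I assume *s* = 0.2, 0.3 or 0.5 mm and *t* = 0.5 or 0.8 mm.

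**Formulas.** With independent frame errors:

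- one frame per session: Var(change) = t² + 2s²
- mean of three frames per session: Var(change) = t² + 2s²/3
- proportional reduction = (4s²/3) / (t² + 2s²)

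**Worked example, s = 0.3, t = 0.5.** One frame: 0.25 + 0.18 = 0.43, SD 0.656 mm. Three frames: 0.25 + 0.06 = 0.31, SD 0.557 mm. Reduction: 0.12/0.43 = 28%.

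| Frame SD s (mm) | t = 0.5 mm | t = 0.8 mm |
|---|---|---|
| 0.2 | 0.0533/0.33 = 16% | 0.0533/0.72 = 7% |
| 0.3 | 0.12/0.43 = 28% | 0.12/0.82 = 15% |
| 0.5 | 0.333/0.75 = 44% | 0.333/1.14 = 29% |

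**Correlated frames.** If errors within a session have correlation *r*, the mean of three has error variance s²[r + (1 − r)/3]. The saving per session is then s²(1 − r)(2/3), so every reduction above is multiplied by (1 − r). At r = 0.5 the rows become about 4% to 8%, 7% to 14% and 15% to 22%.

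**In terms of power.** Let *f* be the share of change-score variance that is momentary. Averaging three independent frames multiplies the variance by 1 − 2f/3. "Subjects will be randomized to receive either Upneeq[™] or balanced saline placebo in both eyes", but no allocation ratio is given, so I assume 57 per arm, a two-sided 5% level and a between-arm comparison of mean change. A difference of 0.525 single-frame SDs then has 80% power with one frame.

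| f | Variance multiplier | SD multiplier | Power with three frames |
|---|---|---|---|
| 0.1 | 0.933 | 0.966 | 82.6% |
| 0.2 | 0.867 | 0.931 | 85.3% |
| 0.3 | 0.800 | 0.894 | 87.9% |
| 0.5 | 0.667 | 0.816 | 92.9% |

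Correlation replaces *f* by f(1 − r), so f = 0.2 with r = 0.5 gives the f = 0.1 row.

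**Why three.** Averaging *m* independent frames removes a fraction 1 − 1/m of the momentary variance: 50% for two, 67% for three, 80% for five. At f = 0.3 the powers are 86.0%, 87.9% and 89.5%. Three is a practical choice, not one that the plan dictates.

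**The case against.** The strongest case on the other side is that the protocol already controls much of what makes lid photographs vary, and that one standardised photograph per session is a defensible choice in a small, resource-limited pilot. Several parts of this stand.

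- A reader might infer that the protocol fixes the count at one frame. It does not. That rests on a singular noun in the outcome sentence. Part 1 uses plurals, though only in general statements, and how the app accepts or rejects a frame is not described. The count is unspecified; one measured frame is what the text yields if followed literally.
- A reader might infer that gaze shifts and all other momentary variation pass undiminished into the change score. Part 1 rules that out for gaze, since subjects fixate on the iPad in primary gaze. Both eyes are also measured. If they are averaged, which the documents do not say, momentary variance is multiplied by (1 + ρ)/2 for between-eye error correlation ρ: 0.5 at ρ = 0, 0.9 at ρ = 0.8 and no dilution at ρ = 1. Blink and brow effects that are largely shared by the two eyes would gain little.
- A reader might infer that the lid change sought must be small compared with the noise. No expected effect is given. The exclusion is only MRD1 below 1 mm, and the earlier trials cited in the Background had a mean baseline of 1.09 mm, so subjects near that mean remain eligible.
- Consecutive frames may share a sustained brow posture, so independence is optimistic. The (1 − r) factor allows for this.

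None of this supplies a replicate or selection rule, and none of it covers partial blink or brow lift.

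**Conclusion.** The point holds as a cheap improvement to the measurement of the primary outcome; the existing outcome definition would not invalidate the trial. As written, residual momentary variation is left unaveraged in each change score, and averaging three frames per time point would reduce it. The saving in variance is 7% to 44% under the assumed SDs and independent frame errors, and about 4% to 22% at a within-session correlation of 0.5. The independent-error figures are upper-end illustrations. The actual gain depends on a frame-to-frame SD that the documents do not give, and it could be modest if that SD is low.

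A reader might go further and infer bias in the treatment effect, either from the noise or from an operator choosing among shots. The documents do not support that. Random noise should be similar in both arms of a randomised comparison. On selection, the distances come from software and the person doing the analysis is blinded. The documents do not say whether the photographer knows the allocation, and nothing shows that shots would be chosen selectively. What can be said is that no rule settles which frame counts; keeping and averaging all frames removes the question.

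**What to change.** Add one sentence to the primary outcome definition and refer to it in Parts 1 and 3 of Procedures Involved: at baseline and at 2 hours, take three consecutive app photographs, with a blink and re-fixation between frames and the brow relaxed; keep all three; use the mean fissure height of the three, for each eye, as the time-point value.

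The cost is a little more time per session and, if one frame is now taken, two more files per session (four per subject over the two sessions). The iPad, the visit and the number of subjects are unchanged. The retained frames would also give the frame-to-frame SD that the plan now lacks, which would help in sizing a later trial.

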Outcome Measure Description: Patient-reported eye appearance will be assessed by patient completion of the FACE-Q Eye Module Survey. These surveys have a total raw score of 7 (worst) to 28 (best). Higher scores indicate greater satisfaction. These survey scores will be

assessed individually. Additionally patients will be queried regarding their perception of the drop including changes in eye appearance before or after drop instillation. Outcome Measure Timeframe: Baseline prior to drop administration, Day 1

Adverse Events and Serious Adverse Events

Treatment-emergent adverse events, defined as any event not present prior to the initiation of the drug treatment or any event already present that worsens in either intensity or frequency following exposure to the drug treatment, will be monitored and reported throughout the study. Treatment emergent adverse scale will be graded as the following:

- Mild: Transient or mild discomfort (<48 hours) to the subject; no medical intervention/therapy required.

- Moderate: Mild to moderate limitation in activity of the subject; no or minimal medical intervention/therapy required.

- Severe: Marked limitation in activity of the subject, some assistance usually required; medical intervention/therapy required including possible hospitalization.

Serious adverse events are defined as those which result in death, hospitalization, persistent or significant incapacity or substantial disruption of the ability to conduct normal life functions (aka disability), or congenital anomaly / birth defect.

Previously reported treatment-emergent adverse effects are described further in the risks section below.

Withdrawal of Subjects

Patients may withdraw at any time at their discretion. Subject withdrawn from and/or terminated from research with or without their consent are those who are found to not meet inclusion/exclusion criteria, and/or are not able to complete the research protocol in its entirety, as well as those who suffer a treatment-emergent adverse effect requiring medication discontinuation. For any subjects who withdraw from research, including partial withdrawal from procedures, study data of the withdrawn subject will not be included in statistical analysis and will be shredded.

Data and Specimen Banking*

Not applicable.

Data Management*

Steps to Secure Data

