The study coordinator will assign each patient a specific ID number and place this information on a separate spreadsheet. The study coordinator will collect the sex, patient's age, and dates of service, but no other identifiable information. No names will be used in the forms. Presentations and publications will not identify individual patients. Data from the subjects' medical records will be encrypted and stored securely as detailed below. Identifiable data will not be stored for future use beyond the timeframe of this study. The release of data will be only to study members and no other outside organization. Data will be kept under lock and key in [name] office at the Bascom Palmer Eye Institute Oculoplastics Research Laboratory on the 4th floor ([name]), data encoded in the computer will be password-protected and will be available only to study personnel, and protected health information will not be re-used or disclosed for other purposes. Study members will be trained on how to log in and log out of the computers. The study coordinator will assign each patient a specific ID number and the sex, patient's age and date of on a separate spreadsheet. The study coordinator will record the study results with the specific sample ID on another spreadsheet.

Statistical Analysis Plan

Statistical analysis will be performed by the researchers. A paired t-test will be used to analyze the difference in palpebral fissure height, eye redness, and patient-reported eye appearance as measured through the FACE-Q survey. 114 subjects will be required to perform perimetric statistics. Chi-squared testing will be used to assess categorical variables. P <0.05 will be considered significant.

Risks to Subjects*

The primary risks to the subjects are adverse reactions to the medication. These risks are explained to patients prior to their arrival to the Oculoplastics Clinic. Previously described potential adverse reactions to include instillation site discomfort, punctate keratitis, and blurry vision although in general is well-tolerated.^{21–23,33} Potential psychosocial risks to subjects include time taken from their day to undergo tests, potentially missing work, and anxiety or discomfort from the eye drop instillation process. This study is not collecting sensitive information, thus no potential risk to reputation or legal risks should occur.

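### Treatment-emergent events are defined against pre-drop status, but no step records symptoms before the drop, and the definition does not clearly cover saline

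*Combined protocol and SAP*

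**What the plan says.** Under Adverse Events and Serious Adverse Events, a treatment-emergent event is "any event not present prior to the initiation of the drug treatment or any event already present that worsens in either intensity". The sentence then extends this to a rise in how often an event occurs, again counted from exposure to the drug, and commits the study to monitoring and reporting such events for its whole duration. The lowest severity grade is brief or slight discomfort that needs no treatment.

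Under Procedures Involved, Part 2, "Subjects will be randomized to receive either Upneeq[™] or balanced saline placebo in both eyes". The patient-reported step in Part 1 is: "Patients will complete a pre-treatment survey to evaluate the perceived baseline eye appearance". The rest of Part 1 is photography and lid measurement. In Part 3, at 2 hours, photographs are repeated and "Patients will complete a post-treatment survey to evaluate the perceived change in eye appearance following" Upneeq use. The paragraph after Part 4 adds: "Patients who do have symptoms concerning any post-procedural complications will be instructed to notify study staff immediately".

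Under Outcomes Measured, within the eye-appearance outcome: "Additionally patients will be queried regarding their perception of the drop including changes in eye appearance before or after drop instillation".

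Risks to Subjects gives the expected reactions as "instillation site discomfort, punctate keratitis, and blurry vision". It separately lists discomfort from having a drop put in, and tells subjects to call about a change in vision, redness or pain. Withdrawal of Subjects includes those with a treatment-emergent effect that requires stopping the medication, and says that withdrawn subjects' study data are left out of the analysis and shredded.

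**The concern.** The definition is a before-and-after comparison, but the before half is not collected for the symptoms that matter. Discomfort and blur are not visible in a photograph and are not measured by an appearance score. A subject who reports irritation at 2 hours cannot be classified as new, worse or unchanged unless someone asked beforehand, and that cannot be reconstructed after the visit.

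The after half relies largely on volunteering, which tends to miss the transient, mild events that make up the lowest grade.

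Any drop can sting or blur, and the protocol itself recognises discomfort from instillation. Only the saline arm can separate that from a drug reaction. A definition worded around drug treatment leaves it to whoever fills in the form whether a saline subject's stinging is classified at all. At stake is the promised safety reporting, not the three efficacy aims.

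**Working it through.** **The definition against the procedures**

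| What the definition needs | What the protocol provides |
|---|---|
| Symptom status before the drop | Appearance survey, photographs, lid measurements. Stable ocular health is an eligibility check, not a symptom record. |
| Symptom status after the drop | Photographs and appearance survey at 2 hours; a drop-perception query with no stated symptom content and no link to adverse events; instructions to notify or call. |
| One rule for both arms | Wording refers to drug treatment only; saline is neither included nor expressly excluded. |
| Events kept once observed | Withdrawn subjects' study data excluded and shredded, including withdrawals for a treatment-emergent effect. |

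Redness is the exception: it is scored from photographs before and after in all subjects, so that one sign has a baseline.

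**Inputs for the size**

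The protocol states no adverse event rate, so there is no figure of this kind to reproduce. The Statistical Analysis Plan gives 114 subjects without an effect size, SD or power; the point does not depend on that number. The allocation ratio is not stated. I assume 1:1, so 114 / 2 = 57 per arm. Event rates and reporting fractions below are also assumptions.

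**Incomplete reporting.** Observed rate = true rate × fraction reported. For a true 10%:
- one quarter reported: 0.10 × 0.25 = 2.5%
- half reported: 0.10 × 0.50 = 5%
- three quarters reported: 0.10 × 0.75 = 7.5%

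**Unclear cover of saline.** Suppose the true rate is 10% in both arms, fully reported. If saline events are classified, the difference is 10% − 10% = 0. If a reader of the definition leaves them out, it appears as 10% − 0% = 10 points. The result would depend on how one sentence is read.

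**Loss through withdrawal.** With 3 events among 57, the rate is 3/57 = 5.3%. If one of those three subjects is withdrawn and removed, it becomes 2/56 = 3.6%.

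**Precision with full capture in both arms.** For equal rates p, the 95% half-width of the difference is 1.96 × √(2p(1 − p)/57):
- p = 5%: 1.96 × √(0.095/57) = 0.080
- p = 10%: 1.96 × √(0.18/57) = 0.110

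For unequal rates, SE = √(p₁(1 − p₁)/57 + p₂(1 − p₂)/57), with power from the two-proportion normal approximation at two-sided 0.05:
- 10% vs 5%: 5 points (−4.6 to 14.6), power 17%
- 20% vs 10%: 10 points (−3.0 to 23.0), power 32%
- 20% vs 5%: 15 points (3.2 to 26.8), power 68%

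**Within the drug arm.** Zero events in 57 gives a one-sided 95% upper bound of 1 − 0.05^(1/57) = 5.1%. Three in 57 gives 5.3% (exact 95% CI 1.1% to 14.6%).

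**The case against.** The strongest defence is that safety is not a stated aim or outcome. This is a self-described pilot with one application of an approved product, and the protocol promises to monitor and report events, not to estimate comparative rates. That stands, and it keeps this at the level of a cheap improvement. The promise to report is still made, though, and is tied to a definition that the procedures cannot feed.

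Three stronger readings are tempting, and the documents do not support them.

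- A reader might infer that nobody asks about anything but appearance after the drop. The drop-perception query exists and its content is not shown, so it could elicit symptoms; all subjects are also told to report symptoms, and redness is scored twice. What is missing is a structured symptom question.
- A reader might infer that saline events are excluded. The protocol uses the product name loosely: Part 2 is headed as Upneeq application yet covers both arms, and the Part 3 survey refers to Upneeq without limiting it to one arm. Drug treatment may be the same shorthand. No monitoring or call instruction is limited to one arm. The fair description is unclear cover, not exclusion.
- A reader might infer that drug-related rates cannot be estimated. A crude count of reported drug-arm events can be made. Its completeness and its excess over saline are what is insecure.

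It is also fair to say that better recording would seldom separate the arms: power is 17% to 32% for 10% vs 5% and 20% vs 10%. The gain is a complete, interpretable table, not a powered test.

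**Conclusion.** The point holds in limited form. Treatment-emergent status depends on a symptom baseline that no listed step records. Post-drop capture rests on an undefined query and self-report, and the definition does not clearly apply to saline. Ascertainment of mild events is therefore likely to be incomplete, and a between-arm comparison is not secured. A crude drug-arm count remains possible.

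The size is illustrative. Half-reporting would turn 10% into 5%. Even full capture leaves a half-width of about 8 to 11 points for the difference at rates of 5% to 10%. These figures rest on an assumed 57 per arm and assumed rates and reporting fractions, none of which the protocol states. The structural finding rests only on its text. The efficacy aims are unaffected.

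**What to change.** 1. Add the same short symptom item (discomfort, blurred vision, pain) to the existing surveys, for every subject, before the drop and at 2 hours. Make it self-completed, or scripted word for word. The examiner applies the drop according to the randomization and only the person doing the analysis is stated to be blinded, so a self-completed item avoids the need for extra blinded staff.
2. Define treatment-emergent as new or worse after instillation of the assigned study drop, Upneeq or saline.
3. Tabulate events by arm, with denominators and confidence intervals.
4. Keep adverse event data from withdrawn subjects, and reword Withdrawal of Subjects so that exclusion and shredding do not apply to those data.

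The cost is about two minutes per subject, one added item at two existing time points and a small amendment, with no extra visit. Two limits remain: precision stays modest, and a symptom item does not assess punctate keratitis, for which the protocol schedules no examination.

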Subjects will be instructed to call immediately for an appointment if they notice a change in their vision, eye redness, or the development of pain in either eye. Care will be taken by all study members to prevent the occurrence of any adverse events.

There are no well-controlled studies of oxymetazoline in pregnant women, and the risks to the fetus or embryo are unknown/unforeseen. One prior publication reported possible renal collecting system abnormalities after using inhaled oxymetazoline³⁴; however, another larger prospective study found no increased risk of malformations associate with nasal inhalant use including oxymetazoline,³⁵ and no alterations in maternal or fetal circulation were found to be associated with oxymetazoline use.³⁶ No studies have been performed evaluating topical oxymetazoline ophthalmic solution. Oxymetazoline is classified as US FDA pregnancy category C.

• US FDA pregnancy category C: Animal reproduction studies have shown an adverse effect on the fetus and there are no adequate and well-controlled studies in humans, but potential benefits may warrant use of the drug in pregnant women despite potential risks.

Participants will be informed of the above information and reserve the right to decline participation in the study. We will not be following pregnancy outcomes.

Unanticipated problems or complications will be reported to the IRB according to posted guidelines.

Risks of the study are listed above and will be minimized by the following:

- Study will be discontinued if subjects experience any negative effect from the medication
- Patients with a known sensitivity or history of adverse reaction to oxymetazoline or similar medications will be excluded from the study

As with any study, there is a risk of confidentiality breach. The research members will assign each patient a specific ID number and place this information on a separate spreadsheet. No names will be used in the forms. Presentations and publications will not identify individual patients.

Potential Benefits to Subjects*

There will be no direct benefit to patients participating in the study. Their involvement may provide satisfaction for aiding in future research, particularly if they would be interested in personally using the agent to increase their own palpebral fissure height or eye redness in the future.

Vulnerable Populations*

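### The serious adverse event definition has no life-threatening, sight-threatening or intervention-to-prevent criterion, so some averted events can be recorded as non-serious

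*Combined protocol and SAP*

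**What the plan says.** The section Adverse Events and Serious Adverse Events defines seriousness once: "Serious adverse events are defined as those which result in death, hospitalization, persistent or significant incapacity or substantial disruption", continuing "of the ability to conduct normal life functions (aka disability), or congenital anomaly / birth defect". The sentence ends there.

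The same section has a separate three-level severity scale. Its top grade is "Severe: Marked limitation in activity of the subject, some assistance usually required; medical intervention/therapy required including possible hospitalization". Nothing links that grade to seriousness. Treatment-emergent events of any grade "will be monitored and reported throughout the study".

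The section Risks to Subjects adds two relevant statements. Subjects are told to "call immediately for an appointment if they notice a change in their vision, eye redness, or the development of pain in either eye". On reporting, it says: "Unanticipated problems or complications will be reported to the IRB according to posted guidelines".

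**The concern.** Every criterion in the definition depends on an outcome that the event produced. None covers harm that was threatened and then averted by treatment. Two examples are an acute hypersensitivity reaction reversed in an emergency room, and an acute eye event that endangered sight, was treated as an outpatient and recovered. Neither has a criterion of its own.

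The setting makes this more than a drafting matter. The route the protocol foresees for an eye complaint is an appointment, and Procedures Involved places any examination after the procedure at the eye institute. Hospitalization is therefore a weak marker of seriousness for the eye events one would most want to know about. Subjects must have stable ocular health, are treated in both eyes, and are told to expect no direct benefit. A later statement that no serious adverse events occurred would naturally be read as excluding life-threatening and sight-threatening events. Under the present wording it would not exclude them.

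**Working it through.** No arithmetic applies, and the plan gives no figure on this point to reproduce. The check is of the text.

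**1. Apply the definition to an averted threat to life or sight.** Assume that death and birth defect do not arise.

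| Course of the event | Criterion met as written | Result |
|---|---|---|
| Admitted to hospital | Hospitalization | Serious |
| Not admitted; significant incapacity or substantial disruption, even if brief | Incapacity or disruption | Serious, if judged significant or substantial |
| Not admitted; no significant incapacity and no substantial disruption | None | Can be recorded as non-serious |

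Only the third row is the gap.

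**2. Does the incapacity have to last?** The definition joins persistent and significant with an *or*, then adds substantial disruption as a further alternative. The parenthesis equating this with disability may hint at duration, but it does not cancel the alternatives. A short episode can therefore qualify, and an event that actually causes significant visual loss may qualify as incapacity.

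**3. Does the severity scale close the gap?** The Severe grade asks for marked limitation of activity together with medical intervention; admission is only a possibility. Marked limitation overlaps with significant incapacity, so many Severe events could already count as serious in the second row. Events in the third row cause no significant incapacity, so they may not reach the Severe grade either. The grade is then not a reliable substitute for the missing criterion.

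**4. Is there a criterion elsewhere?** No other section supplies a criterion for life-threatening or sight-threatening events, or for intervention to prevent a listed outcome. The instruction "Subjects will be instructed to call immediately for an appointment if they notice a change in their vision, eye redness" prompts contact but is not tied to seriousness. The known reactions are given as "instillation site discomfort, punctate keratitis, and blurry vision although in general is well-tolerated", without frequencies and without classification.

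**5. What depends on the label?** The Objectives and Outcomes Measured sections name no safety aim or safety outcome. The Statistical Analysis Plan section contains no analysis of serious events. No reporting timeline is attached to the serious label. The discontinuation statement under Risks to Subjects refers to any negative effect, not to serious events. The effect is therefore confined to how an event is classified and counted.

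**The case against.** The strongest reply is that little follows from the omission. All treatment-emergent events are to be graded and reported whatever their label, the route to the IRB does not depend on the label, and no analysis or timeline uses it. A too favourable safety conclusion would need a reader who saw only a count of serious events, and the protocol does not plan such a count. All of this stands and limits the consequence to misclassification. It does not supply the missing criterion.

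A reader might go further and infer that any Severe reaction treated without admission and leaving no permanent disability is automatically non-serious, or that the definition would miss every acute event of this kind. The documents do not support either reading. The incapacity criterion does not require permanence, and its wording overlaps with the Severe grade. Whether a brief episode counts as significant is left to judgement, which is itself a reason for an explicit criterion.

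It can also be said that the change would not by itself secure complete safety reporting. Under Withdrawal of Subjects, those who cannot complete the protocol, or whose adverse effect requires discontinuation, have their study data left out of the analysis and shredded. A subject who reacts during the 2-hour wait could fall under that rule whatever the label. That is correct, and it is a separate problem that needs its own remedy.

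**Conclusion.** The concern holds within limits. The definition is closed, is based on outcomes reached, and omits events that threaten life or sight or that need intervention to prevent a listed outcome. Such an event can be recorded as non-serious when it is averted without admission and without significant incapacity or substantial disruption. It would still be graded and reported as a treatment-emergent event.

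The size cannot be expressed as a rate. The documents give neither an expected frequency of such events nor an allocation ratio for the approximately 114 subjects, so any percentage would rest on an invented event. Few events are likely, given one application visit and the mild local reactions listed. The effect is on safety classification only; no efficacy estimate, error rate or sample size changes.

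The conclusion assumes that the definition is applied as written and that no other document in use at the site adds a seriousness criterion.

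**What to change.** Extend the seriousness sentence in Adverse Events and Serious Adverse Events so that an event is also serious if it *is life-threatening*, *is sight-threatening*, or *requires medical intervention to prevent one of these outcomes*. State that it applies to both arms. This is worth saying because the treatment-emergent definition in the same section speaks only of exposure to the drug treatment, which leaves the saline arm unclear. Carry the same wording into whatever record is used for adverse events.

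The cost is one sentence. The small downside is that an occasional event treated as an outpatient will be labelled serious. The change affects classification only and leaves the treatment of subjects as it is.
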